5.2 STEP 2 REGISTRATION (Randomization)

An e-mail notification from the SWOG Statistical Center should be received within 10 business days of submitting tissue as described in [Section 15.2](#).

The following additional criteria must be met in order for a patient to be considered eligible for registration to the randomized trial. Any potential eligibility issues should be addressed to the Data Operations Center in Seattle at [contact] prior to registration.

- a. Patients must not be registered until receiving confirmation from the SWOG Statistical Center that the patient's tissue specimen was adequate for PD-L1 testing. Patients must be registered within 7 working days of receiving the e-mail notification.
- b. Women of childbearing potential must plan to have a urine or serum pregnancy test within 72 hours prior to receiving the first dose of study medication. If the urine test is positive or cannot be confirmed as negative, a negative serum pregnancy test will be required.
- c. No tests or exams are required to be repeated for Step 2 registration (Randomization). However, patients who are known to have a change in eligibility status after Step 1 registration are not eligible for Step 2 registration. For example, ANC is not required to be repeated between Step 1 and Step 2 registration, but the most recent ANC performed before Step 2 registration is required to be $\geq 1,500$ mcL.

6.0 STRATIFICATION FACTORS

Patients will be randomized between Arm 1 – physician/patient choice of either high dose interferon or ipilimumab and Arm 2 – MK-3475 (pembrolizumab) in a 1:1 fashion, using a randomized block design. Stratification is based on:

- 1) surgically resected AJCC stage:
IIIA (N2a) versus IIIB versus IIIC versus IV
- 2) PD-L1 status (see [Section 15.2](#)): positive versus negative versus indeterminate
(NOTE: Institutions will be blinded to the patient's PD-L1 status.)
- 3) Planned control arm regimen *: high dose interferon versus ipilimumab.

* NOTE: The intended control arm regimen must be declared prior to randomization for all patients.

7.0 TREATMENT PLAN

For treatment or dose modification questions, please contact [name] at [name] (or [contact]). For dosing principles or questions, please consult the SWOG Policy #38 "Dosing Principles for Patients on Clinical Trials" at <http://swog.org> (then click on "Policies and Procedures" under the "About" menu and choose Policy 38).

7.1 Treatment

a. Pretreatment Labs:

Blood samples collected for pretreatment laboratory tests must be collected and analyzed no more than 3 days prior to dosing. Albumin, glucose, and electrolytes (Na, K, HC03 or CO2) are required within 3 days prior to dosing to obtain baseline data for future toxicity assessments.

b. Arm 1: **Physician/Patient Choice of Either High Dose Interferon or Ipilimumab**

1. High Dose Interferon

Induction Therapy

Agent	Dose Schedule	Route	Days
Interferon Alfa-2b	20 MU/m ² /d* Weeks 1 - 4	IV over 20 min	1-5 5 days a week

* Dose rounding \pm 10% is allowable per institutional standards.

For the purpose of data reporting, 1 cycle = 6 weeks (4 weeks of HDIFN plus first 2 weeks of IFN maintenance.).

If possible, on the days when patients are required to come in for a clinic visit, Interferon treatment should be administered after all questionnaires, procedures and assessment have been completed.

Interferon doses must be rounded to the nearest 1 million unit. Interferon is given over a 20 minute infusion. Day 1 of each week of induction therapy should be administered at the registering institution. Days 2 – 5 of interferon administration for Weeks 1 - 4 may be administered at an institution other than the registering institution provided that during treatment to-date, the patient has not encountered any life-threatening or unusual toxicities and that the registering physician still retains primary responsibility for the patient's treatment. Documentation concerning all drugs administered, side effects, and tests performed must be forwarded to the registering institution. Home Health Agencies (HHA) may be used to treat patients. The registering institution must document any care given at an outside institution.

Maintenance Therapy

Agent	Dose Schedule	Route	Days
Interferon Alfa-2b	10 MU/m ² /d* Weeks 5 - 52	SC	1, 3, 5 M,W,F

For the purpose of data reporting, Cycle 2 (Weeks 7-12) is 6 weeks, and all subsequent cycles are 12 weeks.

Self-Administration of Subcutaneous Doses

Interferon doses must be rounded to the nearest 1 million unit. Patients who are deemed competent to self-administer the subcutaneous maintenance doses of Interferon alfa-2b may do so following the first 4 weeks of treatment. Patients must complete compliance documentation ([Section 7.3](#)) for self-administered doses. If patient cannot self-administer, a nurse, or qualified HHA staff may administer the injections. The registering institution must document any care given at an outside institution.

* Dose rounding \pm 10% is allowable per institutional standards.

2. Ipilimumab

Induction Therapy

Agent	Dose Schedule	Route	Days
Ipilimumab	10 mg/kg* Weeks 1-10; weeks total of doses	IV infusion over 90 minutes	1 Q 3 for a four

For the purpose of data reporting, 1 cycle = 6 weeks.

* Dose rounding \pm 10% is allowable per institutional standards.

If possible, on the days when patients are required to come in for a clinic visit, treatment should be administered after all questionnaires, procedures and assessment have been completed.

The final concentration must be between 1-2 mg/mL.

Maintenance Therapy

Agent	Dose Schedule	Route	Days
-------	---------------	-------	------

Ipilimumab 10 mg/kg* IV infusion 1 Weeks
25-145; over 90 Q 12
weeks minutes for 11
doses ending
at 3 years)

For the purpose of data reporting, 1 cycle = 12 weeks.

* Dose rounding \pm 10% is allowable per institutional standards.

If possible, on the days when patients are required to come in for a clinic visit, treatment should be administered after all questionnaires, procedures and assessment have been completed.

The final concentration must be between 1-2 mg/mL.

c. Arm 2: **MK-3475 (Pembrolizumab)**

Agent	Dose	Route	Schedule
MK-3475 weeks (Pembrolizumab)	200 mg	IV over 30 minutes	Day 1, Q 3 for 52 weeks

For the purpose of data reporting, Cycle 1 and Cycle 2 are 6 weeks and all subsequent cycles are 12 weeks.

MK-3475 (pembrolizumab) treatment should be administered after all questionnaires, procedures and assessments have been completed. MK-3475 (pembrolizumab) treatment may be administered up to 3 days before or after the protocol-specified Q 3 weeks due to administrative reasons.

MK-3475 (pembrolizumab) treatment will be administered on an outpatient basis.

MK-3475 (pembrolizumab) will be administered as a 30 minute IV infusion. Infusion timing should be as close to 30 minutes as possible; however, a window of -5 minutes and +10 minutes is permitted (*i.e.*, infusion time is 25-40 minutes).

Dosing interruptions are permitted in the case of medical / surgical events or logistical reasons not related to study therapy (e.g., elective surgery, unrelated medical events, patient vacation, and/or holidays). Patients should be placed back on study therapy within 3 weeks of the scheduled interruption, unless otherwise discussed with the Study Chairs. The reason for interruption should be documented in the patient's study record.

All planned doses must be administered. Missed doses must be made up.

7.2 Prohibited and Cautionary Medications

Radiation therapy must be completed at least 1 day prior to starting ipilimumab or MK-3475 and must be completed at least 7 days prior to starting interferon.

Patients are prohibited from receiving the following therapies after registration to Step 1 and through completion of protocol therapy:

- Anti-cancer systemic chemotherapy or biological therapy.
- Immunotherapy not specified in this protocol.
- Any non-study anti-cancer agent (investigational or non-investigational).
- Investigational agents other than MK-3475.
- Live vaccines: Examples of live vaccines include, but are not limited to, the following: measles, mumps, rubella, chicken pox, shingles, yellow fever, rabies, BCG, and typhoid (oral) vaccine. Seasonal influenza vaccines for injection are generally killed virus vaccines and **are allowed**; however, intranasal influenza vaccines (e.g. Flu-Mist[®]) are live attenuated vaccines, and are not allowed.
- Glucocorticoids for any purpose other than to modulate symptoms from an event of suspected immunologic etiology. The use of physiologic doses of corticosteroids (defined as 10 mg prednisone) are acceptable, however site investigators should consult with the Study Chair for any dose higher than 10 mg prednisone.

Patients who, in the assessment by the investigator, require the use of any of the aforementioned treatments for clinical management should be removed from protocol treatment. Patients may receive other medications that the investigator deems to be medically necessary.

7.3 Drug Compliance Documentation

Patients who self-administer interferon alfa-2b, may complete the **S1404** Patient Interferon Diary which can be found in [Section 18.3](#). Institutional CRAs will review and ascertain patient adherence with protocol therapy at the end of treatment for each cycle. The completed patient diary should be kept in the patient's clinic chart. Note that the diary is provided only as a tool for tracking patient compliance. Do not submit patient diaries to the SWOG Data Operations Office. Sites may utilize institutional diaries or other source documentation in place of the **S1404** Patient Interferon Diary at the discretion of the treating physician. The completed Interferon Diary, institutional diary, or other source documentation in place of the **S1404** Interferon Diary must be available for upload if requested as part of the risk based monitoring.

7.4 Criteria for Removal from Protocol Treatment

- a. Recurrence of disease (as defined in [Section 10.0](#)).
- b. Unacceptable toxicity.
- c. The patient may withdraw from the study at any time for any reason.
- d. The investigator may discontinue treatment if they determine that the patient's continued treatment on the study is detrimental to their long-term health, or due to poor compliance with the study's required visits and treatments.
- e. Positive pregnancy test.
- f. Completion of protocol treatment.
- g. Patients will be removed from protocol treatment if there is a treatment delay > 84 consecutive days for any reason.

7.5 Discontinuation of Treatment

All reasons for discontinuation of treatment must be documented in the Off Treatment Notice.

7.6 Follow-Up Period, End of Study

Randomized patients will be followed until death or 10 years after randomization, whichever occurs first.

8.0 TOXICITIES TO BE MONITORED AND DOSE MODIFICATIONS

8.1 NCI Common Terminology Criteria for Adverse Events

This study will utilize the CTCAE (NCI Common Terminology Criteria for Adverse Events) Version 5.0 for toxicity and Serious Adverse Event reporting. A copy of the CTCAE Version 5.0 can be downloaded from the CTEP home page (<http://ctep.cancer.gov>). All appropriate treatment areas should have access to a copy of the CTCAE Version 5.0.

8.2 Dose Modification Considerations for Patients Receiving Interferon (Arm 1)

a. General

Induction therapy by the IV route in Weeks 1-4 shall be evaluated separately from Maintenance therapy in Weeks 5-52. A patient requiring dose modification(s) in the first 4 weeks will therefore commence Week 5 at full dose. **Doses missed during treatment due to toxicity, patient compliance, holiday, etc. should not be made up.**

b. Arm 1 – IFN Dose Modification Table

	Full Dose	Dose mod 1	Dose mod 2	Dose mod 3
Induction (Weeks 1-4)	20 MU/m ²	13.3 MU/m ²	6.6 MU/m ²	Remove from protocol treatment
Maintenance (Weeks 5-52)	10MU/m ²	6.6 MU/m ²	3.3 MU/m ²	Remove from protocol treatment

PLEASE NOTE: If a patient experiences any of the toxicities listed below, the patient must have a dose modification as follows: treatment must be held until the toxicity returns to institution's normal limits, patient's baseline, or normal limits per CTCAE or as listed in the table under [Section 8.2c](#), then reduced per above.

EXCEPTIONS: For Grade 3 proteinuria without creatinine or BUN elevation, dose should be held until return to Grade 2 toxicity. For Grade 2 weight loss observed over a period of one month, dose should be held until weight gain or stabilization.

Dose modifications outside of the guidelines prescribed below are allowed at the discretion of the treating physician if:

- The modification is being performed due to toxicity related to HDI therapy; and,
- After consideration of the patient's safety and overall clinical status, the treating physician feels that the modification is in the patient's best interest.

Any modifications outside of the prescribed guidelines must be documented in the comment section of the [S1404](#) Treatment Form.

c. ARM 1 (IFN) TOXICITIES TO BE MONITORED AND DOSE MODIFICATIONS (24)

TOXICITY	GRADE 2	GRADE 3	GRADE 4
Blood/Bone Marrow Thrombocytopenia Anemia Neutropenia	Full Dose	Hold therapy*; Reduce one dose level	Remove from protocol treatment
	Hold therapy* until return to Grade 1 or baseline; reduce one dose level	Hold therapy* until return to Grade 1 or baseline; reduce one dose level	Remove from protocol treatment
	Full Dose	Full Dose	Reduce one dose level
Cardiovascular Arrhythmia Cardiac-Other	Hold therapy until return to normal*; reduce one dose level after formal cardiologic evaluation and clearance	Removal from protocol treatment	Removal from protocol treatment
Gastrointestinal Nausea, vomiting and/or diarrhea Weight loss	Administer supportive care; if persistent for more than 2 weeks, reduce one dose level	Hold therapy*; reduce one dose level	Removal from protocol treatment
	Hold therapy for weight loss observed over a 1 month period until weight gain or stabilization*		
Hepatic ALK PHOS. Bilirubin or SGOT(AST)/SGPT (ALT)	Full Dose	Hold therapy until return to \leq Grade 1*; reduce one dose level	Removal from protocol treatment
Neurology Cognitive disturbance Mood alteration Neuropathy – motor	Full Dose	Hold therapy*; reduce one dose level (evaluation by specialist)	Removal from protocol treatment

TOXICITY	GRADE 2	GRADE 3	GRADE 4
Neuropathy - sensory			
Renal/Genitourinary Proteinuria Creatinine	Full Dose Hold therapy*; reduce one dose level	Hold therapy until return to ≤ Grade 2*; reduce one dose level Removal from protocol treatment	Removal from protocol treatment Removal from protocol treatment

***PLEASE NOTE:** If a patient experiences any of the toxicities listed in the above table, the patient must have a dose modification as indicated (unless otherwise specified). Treatment must be held until the toxicity returns to institution's normal limits, patient's baseline, or normal limits per the Common Terminology Criteria for Adverse Events v5.0 (CTCAE) at <http://ctep.cancer.gov>, then reduce as indicated above. Dose re-escalation will not be attempted following resolution of toxicity that required dose interruption or attenuation.

8.3 Dose Modification Considerations for Patients Receiving Ipilimumab (Arm 1)

a. Dose and schedule modifications for ipilimumab

There will be no dose reductions for ipilimumab. The dose of ipilimumab will either be given or delayed/discontinued. Patients may develop study drug-related toxicities that may require skipping doses or dose discontinuation. Some of these adverse events may be consistent with potentially drug-related immune-mediated phenomena; termed IRAEs. Details of how to dose study medication in the presence of adverse drug reactions that may or may not be IRAEs are addressed below.

Patients will delay or discontinue treatment with ipilimumab if they experience at least one adverse event, specified below, considered by the investigator to be **definitely, probably, or possibly** related to ipilimumab treatment unless otherwise specified. The following criteria will be used to determine dosing delay, restarting doses, or discontinuing ipilimumab. For an adverse event, review the following criteria in a stepwise manner: First, assess the dose delay criteria and decide whether a scheduled dose should be delayed. Second, determine whether the permanent discontinuation criteria apply to the adverse event in question as well.

NOTE: Due to the possible effect of treatment with ipilimumab on the immunologic response to infectious disease vaccines, patients must not have had any infectious disease vaccination (e.g., standard influenza, H1N1 influenza, pneumococcal, meningococcal, tetanus toxoid) 1 week before or after any dose of ipilimumab.

b. Criteria to delay/skip one dose of ipilimumab

**NOTE: See also: [Section 8.3e](#): Dose Modification and Management for Cardiomyopathy Myocarditis

Delay ipilimumab dosing for any of the following definitely, probably, or possibly treatment related adverse events, unless otherwise specified:

- Grade ≥ 1 diarrhea and/or colitis **regardless of attribution**. Grade ≥ 2 diarrhea and/or colitis, definitely, probably, or possibly related to ipilimumab, requires permanent discontinuation.
- Any other \geq Grade 2 non-skin related adverse event (including IRAEs) except for laboratory abnormalities.
- Grade ≥ 2 laboratory abnormalities that are secondary to an immune-related adverse event or autoimmune phenomenon (e.g., Grade ≥ 2 TSH associated with a CTCAE v.4 grade 2 thyroid dysfunction induced by ipilimumab, anemia, neutropenia, amylase, lipase, CPK, hyperglycemia, or elevated LFTs) should also lead to an ipilimumab dosing delay/skipping.
- Any other \geq Grade 3 laboratory abnormality.
- Any \geq Grade 3 skin-related adverse event (including IRAEs) **regardless of attribution**.

c. Criteria to resume ipilimumab treatment

**NOTE: See also: [Section 8.3e](#): Dose Modification and Management for Cardiomyopathy Myocarditis

Ipilimumab **may not** be restarted while the patient is being treated with oral or intravenous corticosteroids for the management of immune related adverse events except for patients on stable doses of hormone replacement therapy for adrenal insufficiency such as hydrocortisone. In addition, patients must be off and have no requirement for oral/I.V. corticosteroids for at least 1 week and meet the other criteria for retreatment as outlined below.

Restart ipilimumab dosing if/when the adverse event(s) resolve(s) to \leq Grade 1 severity or returns to baseline within 3 weeks of last dose administration:

- If the adverse event has resolved (to \leq Grade 1 severity or returns to baseline), restart ipilimumab dosing at the next scheduled time point per protocol.
- If the adverse event has not resolved in the protocol-specified dosing window, the next scheduled dose will be omitted.
- Patients with Grade 1 diarrhea and/or colitis who require steroid therapy must have resolution to Grade 0 (or baseline) before resuming dosing with ipilimumab. Patients with Grade \geq 2 related diarrhea and/or colitis must have ipilimumab permanently discontinued.

d. Criteria for permanent discontinuation of ipilimumab for Related Adverse Events

**NOTE: See also: [Section 8.3e](#): Dose Modification and Management for Cardiomyopathy Myocarditis

Ipilimumab administration must be permanently discontinued for any of the following definitely, probably, or possibly treatment related adverse events, unless otherwise specified:

- Any \geq Grade 2 eye pain or reduction of visual acuity that does not respond to topical therapy and does not improve to \leq Grade 1 severity within 2 weeks of starting therapy, OR, requires systemic treatment.
- Any \geq Grade 2 diarrhea and/or colitis related to ipilimumab. Any \geq Grade 2 diarrhea/colitis should be considered RELATED unless immune related colitis is definitely ruled out (including by endoscopy and biopsy.)
- Any \geq Grade 2 hypophysitis, pneumonitis, nephritis, and/or sarcoid-like lesions.
- Any new motor or sensory neurologic toxicity \geq Grade 2 regardless of attribution (including Guillain-Barré syndrome and myasthenia gravis).
- Any \geq Grade 3 bronchospasm or other hypersensitivity reaction.
- Any other \geq Grade 3 non-skin adverse event with the exception of events listed under “Exceptions to Permanent Discontinuation”
- AST or ALT $> 5 \times$ ULN.
- Total Bilirubin $> 3 \times$ ULN.
- Any other \geq Grade 4 laboratory abnormalities except for specified exceptions
- Any other \geq Grade 4 adverse event.
- Stevens-Johnson syndrome, toxic epidermal necrolysis, or rash complicated by full thickness dermal ulceration or necrotic, bullous, or hemorrhagic manifestations.
- Any adverse event, laboratory abnormality or intercurrent illness which, in the judgment of the investigator, presents a substantial clinical risk to the patient with continued dosing.
- Patients who require high dose steroids, other immune suppressants or anti-TNF drug therapy for the management of immune related adverse

events as described in the Toxicity Management Guidelines/Algorithms should have ipilimumab permanently discontinued.

e. Dose Modification and Management for Cardiomyopathy Myocarditis

- Drug will be held for Grade 2 cardiac dysfunction pending evaluation
- Drug will be permanently discontinued for Grade 3 or 4 cardiac dysfunction and Grade 2 events that do not recover to baseline or that reoccur
- Treatment with steroids as clinically indicated

Cardiac *	Management/Next Dose for BMS-936558 (Nivolumab) + Ipilimumab Cardiac Toxicities
≤ Grade 1	Hold dose pending evaluation and observation.** Evaluate for signs and symptoms of CHF, ischemia, arrhythmia or myositis. Obtain history EKG, CK (for concomitant myositis), CK-MB. Repeat troponin, CK and EKG 2-3 days. If troponin and labs normalize may resume therapy. If labs worsen or symptoms develop then treat as below. Hold pending evaluation.
Grade ≥2 with suspected myocarditis	Hold dose.** Admit to hospital. Cardiology consult. Rule out MI and other causes of cardiac disease. Cardiac Monitoring. Cardiac Echo. Consider cardiac MRI and cardiac biopsy. Initiate high dose methylprednisolone. If no improvement within 24 hours, add either infliximab, ATG or tacrolimus. Resume therapy if there is a return to baseline and myocarditis is excluded or considered unlikely.
Grade ≥2 with confirmed myocarditis	Off protocol therapy. Admit to CCU (consider transfer to nearest Cardiac Transplant Unit). Treat as above. Consider high dose methylprednisolone. Add ATG or tacrolimus if no improvement. Off treatment.

*Including CHF, LV systolic dysfunction, Myocarditis, CPK, and troponin
 
**Patients with evidence of myositis without myocarditis may be treated according as "other event"
 
Note: The optimal treatment regimen for immune mediated myocarditis has not been established. Since this toxicity has caused patient deaths, an aggressive approach is recommended.
	

f. Exceptions to permanent discontinuation of ipilimumab

Ipilimumab administration may be resumed in the following cases:

- Potentially reversible inflammation (< Grade 4), attributable to a local anti-tumor reaction and a potential therapeutic response. This includes inflammatory reactions at sites of tumor resections or in draining lymph nodes, or at sites suspicious for, but not diagnostic of metastasis.
- Laboratory abnormalities that are rapidly reversible, not life threatening, do not reflect underlying organ system dysfunction, and are not related to the study treatment, such as transient elevations of uric acid, hypocalcaemia, hypophosphatemia.
- Hospitalization for ≤ Grade 2 adverse events (not including Grade 2 events that require permanent discontinuation) where the primary reason for hospitalization is to expedite the clinical work-up.
- Patients with the following conditions where in the investigator's opinion continuing study drug administration is justified:
 - Ocular toxicity that has responded to topical therapy and has improved to ≤ Grade 1 severity within 2 weeks of starting therapy.
 - Patients without a diagnosis of hypophysitis who have Grade 2 hypothyroidism, Grade 2 low testosterone or Grade 2 adrenal insufficiency where clinical symptoms are controlled with appropriate hormone replacement therapy.

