9.2 Arm 1: Ipilimumab (contd.)

		ON TREATMENT ^a																					
		Pre-Study Screening		Randomization		Induction		C		C		C		C		C		C		C			
		Reg Step 1	Reg Step 2	Cy 1	Cy 2	3	4	5	C6	7	8	9	10	11	12	13	14	15	16	17	18	19	
*				W	W	W	W	W	W	W	W	W	W	W	W	W	W	W	W	W	W	W	
	X-RAYS AND SCANS			1	4	7	10	13	25	37	49	61	73	85	97	109	121	133	145				
	Whole body PET/CT or CT neck, chest, abdomen & pelvis ^k	X				X	X	X															
	Brain MRI or CT with contrast ^k	X																					
	EKG ^h	X																					
	Image Submission ^p	X				X	X	X															
	SPECIMEN SUBMISSION																						
	Slides for PD-L1 expression ^l	X																					
	E-mail confirmation tissue was adequate for PD-L1 analysis																						
	Tissue ^m for banking	X																					
	Serum ^m for banking	X ⁿ																					
	Plasma & Buffy Coat ^m for RNA/DNA for banking																						
	TREATMENT			X	X	X	X			X	X	X	X	X	X	X	X	X	X	X	X	X	
	Ipilimumab																						

[Click here for footnotes.](#)

NOTE: Forms are found on the protocol abstract page of the SWOG website (www.swog.org). Form submission guidelines are found in [Section 14.Q](#).
 NOTE: Unless indicated otherwise in the protocol, scheduled procedures and assessments (treatment administration, toxicity assessment for continuous treatment, disease assessment, specimen collection and follow-up activities) must follow the established SWOG guidelines as outlined in <https://www.swog.org/sites/default/files/docs/2017-10/Best%20Practices%20update.pdf>.

Footnotes for Study Calendar 9.2: Arm 1 Ipilimumab

- a. The following exams and labs are performed prior to receiving first dose and at the start of every cycle until end of protocol treatment: physical (w BSA, BP & WT), PS, toxicity notation, ANC, platelets, Hgb, total bilirubin, AST and ALT, alk phos, serum creatinine or CrCl, albumin, glucose, Na, K, HCO₃ (or CO₂). Adverse Event Assessments on the study will continue for all patients until 30 days after the last study drug administration. However, patients with ongoing toxicities should be seen more often as clinically indicated.
- b. End of treatment assessment occurs at the 15th infusion or whenever patient comes off treatment (treatment stops at the end of Year 3, even if the patient has not received all 15 infusions).

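### Section 8.3c ties ipilimumab restart to recovery within 3 weeks of the last dose, which fits only 3 of the 14 dosing intervals and disagrees with the section's own bullets

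*Combined protocol and SAP*

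**What the plan says.** Section 8.3c governs when ipilimumab may be resumed after an adverse event. Its lead sentence allows restart if or when the event resolves to at most "Grade 1 severity or returns to baseline within 3 weeks of last dose administration". Two bullets follow that bear on timing:

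- If the event has resolved, sites are to "restart ipilimumab dosing at the next scheduled time point per protocol". No time limit is attached.
- "If the adverse event has not resolved in the protocol-specified dosing window, the next scheduled dose will be omitted". The protocol text states no such window for ipilimumab.

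A separate condition concerns steroids: "patients must be off and have no requirement for oral/I.V. corticosteroids for at least 1 week". It adds a requirement but does not bear on the 3-week limit.

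Section 7.1b gives four induction doses 3 weeks apart (Weeks 1 to 10), then 11 maintenance doses 12 weeks apart (Weeks 25 to 145). Calendar 9.2 agrees: "End of treatment assessment occurs at the 15th infusion or whenever patient comes off treatment".

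Two other sections could have settled the matter. Section 8.3d lists the events that require permanent discontinuation; recovery later than 3 weeks is not among them. Section 7.4g removes a patient from protocol treatment when a delay exceeds 84 days in a row, for any reason.

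**The concern.** The 3-week limit equals the induction interval. There, recovering within 3 weeks of the last dose means the same as recovering by the next one. In maintenance the two come apart: the limit runs out long before the next dose is due, while the first bullet still tells the site to restart anyone who has recovered.

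The two readings lead to opposite dosing decisions for the same patient. Ipilimumab is one of the two control regimens, and 11 of its 15 planned doses are maintenance doses. If sites differ, ipilimumab exposure and the off-treatment reasons recorded under Section 7.5 will partly reflect how each site read the paragraph. The toxicity rates planned for each control regimen in Section 11.7b describe patients with that exposure.

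**Working it through.** No statistical formula applies. The check is a count of the schedule, followed by a comparison of the rules.

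**1. Reproduce the planned number of infusions.** From Section 7.1b:

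- Induction weeks: 1 + 3i for i = 0 to 3, giving 1, 4, 7, 10.
- Maintenance weeks: 25 + 12i for i = 0 to 10, giving 25, 37, 49, 61, 73, 85, 97, 109, 121, 133, 145.

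That is 4 + 11 = 15 doses, the last at Week 145. Both figures match calendar 9.2.

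**2. Intervals between doses.** Fifteen doses give 14 intervals.

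| Interval | Number | Length | Time from end of 3-week limit to next dose |
|---|---|---|---|
| Within induction | 3 | 3 weeks | 0 |
| Week 10 to Week 25 | 1 | 15 weeks | 12 weeks |
| Within maintenance | 10 | 12 weeks | 9 weeks |

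The limit coincides with the next dose in 3 of 14 intervals. In the other 11 (11/14 = 79%) it ends 9 or 12 weeks earlier. In total, 12 + 10 × 9 = 102 of the 144 weeks between first and last dose (71%) lie beyond the limit. This is a share of the planned calendar, not of patients or events.

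**3. An event between maintenance doses.** Take a related Grade 2 event, of a kind that triggers a delay under 8.3b but is not on the 8.3d list. It starts 4 weeks after a maintenance dose and resolves 2 weeks later.

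- Recovery comes 4 + 2 = 6 weeks after the last dose, and 12 − 6 = 6 weeks before the next.
- Lead sentence: 6 weeks exceeds 3, so the condition is not met.
- First bullet: the event has resolved, so restart at the next scheduled dose.
- Section 8.3d: nothing requires discontinuation.

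**4. An event still present when a dose is due.** The last dose was at Week 25, the event is unresolved at Week 37, and it resolves at Week 40.

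- Second bullet: the Week 37 dose is omitted. No later dose is mentioned.
- First bullet: once resolved, restart at Week 49.
- Lead sentence: recovery came 40 − 25 = 15 weeks after the last dose, so the condition is not met.
- Section 7.4g: counted from the missed due date, the delay is 12 × 7 = 84 days. The limit is more than 84, so it is not triggered.

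In both cases the lead sentence and the bullets part ways, and neither 8.3d nor 7.4g decides between them.

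**The case against.** A reader might infer that the rule excludes every patient with a late-onset maintenance event from further ipilimumab. The text does not say so. The lead sentence states when to restart; where the protocol forbids dosing it says so outright, as it does for patients on steroids and for the 8.3d events. What happens to a patient who recovers after 3 weeks is never stated. The 3-week phrase can also be read as qualifying only the return to baseline, in which case resolution to Grade 1 or less counts whenever it occurs. These points stand against the strong reading. They do not remove the ambiguity: if the bullets govern, the 3-week limit has no function, and if it qualifies only the return to baseline, the mismatch persists for patients who qualify by that route.

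A second objection is that an event which starts and ends between doses holds up no dose, so 8.3c never applies. That does not succeed. In induction the 3-week limit covers exactly such events, and the first bullet is addressed to events that have resolved.

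A reader might also put the effect at 75% of maintenance events, since 63 of the 84 days in a 12-week interval fall after day 21. That requires onset to be spread evenly over the interval, and the ipilimumab adverse-event list in Section 3.2 notes that most immune-mediated reactions appeared early in treatment. Many events also never reach 8.3c, because 8.3d requires discontinuation. The figure does not measure impact.

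Nor can it be said that no dosing window exists. A note to calendar 9.2 sends sites to linked SWOG guidelines for treatment administration, and a window may be given there.

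Finally, the primary analysis is by intention to treat (Section 11.5), so differing practice would not change who is analysed in which arm. That is correct, and it limits the consequence to exposure and conduct.

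**Conclusion.** The inconsistency is real and in the current text. The 3-week limit matches 3 of 14 dosing intervals and runs out 9 to 12 weeks before the next dose in the other 11. Read literally, the lead sentence is not met by a patient whom the first bullet tells the site to restart, and neither the discontinuation list nor the 84-day limit settles which governs.

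The count rests on the schedule as planned, without delays. The 84-day comparison assumes that a delay is counted from the missed due date. How many patients meet the conflict cannot be estimated, since the documents give neither onset times nor the proportion reaching maintenance. The documents support a risk of inconsistent conduct in the ipilimumab group, with effects on exposure and off-treatment reasons. They do not support a claim that patients are excluded outright or that the primary comparison is biased. No alpha, power or sample size figure changes.

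**What to change.** The sponsor should reconcile the lead sentence of 8.3c with its two bullets, the maintenance schedule in 7.1b, the discontinuation list in 8.3d and the delay limit in 7.4g, so that a patient who recovers more than 3 weeks after a dose meets one stated outcome. The second bullet should either point to the dosing window it means, including any in the linked SWOG guidelines, or drop the phrase. Which clinical limit should apply is for the sponsor to decide.

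The cost is rewording one paragraph; no procedures are added. If ipilimumab dosing has already finished, the useful step is a short clarification and a check of how sites applied the rule, so that exposure and off-treatment reasons can be interpreted.
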